CLINICAL STUDY PROTOCOL

Version: 1.0

Document Date: October 11, 2023

NCT06232018

Title:

A Comparison of 2-Octyl Cyanoacrylate Skin Adhesive and Polyester Mesh for Wound Closure in Total Knee Arthroplasty: A Randomized Controlled Study

Sponsor:

Hatyai Hospital, Songkhla, Thailand

Principal Investigator:

[name]

Email: [contact]

[contact]

IRB Approval:

HYH EC 059-66-01

1. Background and Rationale

Nowadays, there are many methods of wound closure in Total Knee arthroplasty, such as nylon, skin staple, and sterile strip, which differ in advantages and disadvantages of each technique. However, these methods have the same disadvantages: wound discharge, which may lead to infection, wound separation, and the need for wound dressing. It is also a burden for patients and caregivers. In travelling to change the wound in a hospital, There are many costs in terms of wound dressing equipment, travel costs and time off from work for caregivers to take patients to get wound dressing.

Skin adhesive is an innovation for wound closure in total knee arthroplasty. It reduces the problem of wound separation, with no need for wound dressing.

Skin adhesive mesh has been studied in many studies, showing that it can be used well. Strong It is no different from traditional wound closure; the scar is more beautiful. Patients are more satisfied. But the disadvantage is the high price.

Skin adhesive without polyester mesh has the advantage of being cheaper three times than polyester mesh but less intense than with mesh. This makes it unpopular.

No studies have been found comparing wound dressings with mesh and no mesh After knee replacement surgery.

Therefore, this study is to compare skin adhesive and skin adhesive plus polyester mesh in closure wound total knee arthroplasty.

Are there differences in patient satisfaction Are wound complications such as wound oozing, wound separation, superficial wound skin infection, and contact dermatitis different?

2. Objectives

Primary Objective:

To compare POSAS scores between skin adhesive alone and skin adhesive with polyester mesh at 6 weeks.

Secondary Objectives:

To compare Vancouver Scar Scale scores, wound leakage area (mm²), wound complications, and allergic contact dermatitis.

3. Study Design

Prospective, single-center, randomized controlled parallel-group study with 80 participants randomized 1:1.

4. Eligibility Criteria

Inclusion:

- Age 50–80 years
- Undergoing primary unilateral TKA

Exclusion:

- Prior knee surgery
- Keloid scar history
- Psoriasis at operative site
- Contact dermatitis to adhesive
- Cognitive impairment

5. Randomization and Blinding

Block randomization using block sizes 4 and 6. Allocation concealed with opaque envelopes. Outcome assessor blinded.

6. Interventions

:Every patient received TKA using the same surgical methods and instruments.

Group 1: 2-octyl cyanoacrylate skin adhesive

Group 2: 2-octyl cyanoacrylate skin adhesive + polyester mesh

7. Outcome Measures

Primary:

POSAS total score at 6 weeks.

Secondary:

POSAS score at 3 months

Vancouver Scar Scale (VSS) at 6 weeks.

Wound leakage area measured using 1 mm² grid.

Wound complications: dehiscence, superficial infection, allergic contact dermatitis.

8. Study Procedures and Follow-Up

- Every patient received TKA using the same surgical methods and instruments and received standard postoperative protocol.

- Following subcuticular suturing, patients were randomized into two treatment arms

- All wounds in both groups were then covered with a 20 × 10 cm Waterproof Wound Dressing

- Follow up at 2 weeks post-operative to evaluate wound drainage by placing the waterproof dressing on the table grid, then use a millimeter grid to count the number of grid squares stained with blood. (Wound leakage measurement).

- Scar evaluation at 6 weeks (POSAS, VSS).

9. Statistical Analysis Plan

Continuous variables assessed for normality.

- Mann-Whitney U test for nonparametric outcomes.

- Independent t-test for parametric variables.

Categorical outcomes: chi-square or Fisher's exact test.

Significance level: $p < 0.05$.

10. Ethics

This protocol was approved by the institutional ethics committee (Protocol no. HYH EC 059-66-01) and was conducted in accordance with the Declaration of Helsinki

11. Data Handling and Confidentiality

Participant data will be de-identified and securely stored. Only the research team will have access, and confidentiality will be strictly maintained.

12. Funding

Supported by Hatyai Hospital Research Fund. No commercial funding.

End of Protocol.

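### Does the satisfaction question in the rationale leave the trial without an outcome it needs?

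*Combined protocol and SAP*

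**What the plan says.** The last lines of Section 1 (Background and Rationale) put two questions: "Are there differences in patient satisfaction" and "Are wound complications such as wound oozing, wound separation, superficial wound skin infection, and contact dermatitis different". The only other mention of satisfaction is a background remark, also in Section 1, about earlier experience with mesh.

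Section 2 (Objectives) gives the primary objective as "To compare POSAS scores between skin adhesive alone and skin adhesive with polyester mesh at 6 weeks" and the secondary objectives as "To compare Vancouver Scar Scale scores, wound leakage area (mm²), wound complications, and allergic contact dermatitis". Section 7 (Outcome Measures) names "POSAS total score at 6 weeks" as primary and places "POSAS score at 3 months" among the secondary outcomes, with the Vancouver Scar Scale (VSS), leakage area and three complications. Section 8 treats POSAS and VSS as the scar assessment at 6 weeks. On blinding, Section 5 says only "Outcome assessor blinded". No section describes the content of POSAS or connects it to satisfaction.

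**The concern.** The satisfaction question comes directly after the statement of what the study is for, so it reads as something the trial means to answer. Set against Section 7, it is the only item in the closing questions without a designated measure.

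The worry is a claim shaped after the fact. With no measure named, a statement about satisfaction could later be drawn from the 6-week POSAS total, from the 3-month score, or from a component picked once the data are known. Section 9 gives only general tests at the 5% level and does not address the point. If that happened, the error rate behind the claim would exceed 5%, and the reader could not tell which result had been meant to answer the question.

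**Working it through.** **Step 1. Match the closing questions of Section 1 to Section 7.**

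| Item asked about in Section 1 | Outcome in Section 7 |
|---|---|
| Satisfaction | none labelled |
| Oozing | leakage area |
| Separation | dehiscence |
| Superficial infection | superficial infection |
| Contact dermatitis | allergic contact dermatitis |

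Four of the five items are covered. Satisfaction is mentioned twice in the document, both times in Section 1, and not at all in Sections 2, 7, 8 or 9.

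**Step 2. Match Section 2 to Section 7.** POSAS at 6 weeks, VSS, leakage area, wound complications and allergic contact dermatitis each have an outcome. No objective is left unmeasured. The mismatch lies between the rationale and the objectives, not between the objectives and the outcomes.

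**Step 3. Is there a natural reading?** Section 1 asks about satisfaction first and complications second. Section 2 puts POSAS first and complications later. The background also mentions better-looking scars immediately before more satisfied patients, so the authors associate the two. This makes POSAS the plausible counterpart, but it remains an inference.

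**Step 4. What would a free choice cost?** Suppose satisfaction were claimed from whichever of the two POSAS results reached p < 0.05, with no true difference.

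- Independent results: 1 − 0.95² = 1 − 0.9025 = 9.75%.
- Correlated results, from the bivariate normal probability that at least one |Z| exceeds 1.96: 9.1% at correlation 0.5, 8.3% at 0.7 and 7.0% at 0.9.

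The correlations are assumptions; the protocol gives none. The range applies only if the two results are interchangeable. Section 7 ranks them, with 6 weeks primary and 3 months secondary. Having two POSAS time points is an ordinary multiplicity matter that exists whether or not Section 1 mentions satisfaction.

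**Step 5. What would an added item give?** Section 3 describes a "randomized controlled parallel-group study with 80 participants randomized 1:1", so 40 per arm. With full follow-up, the 95% confidence interval for a difference in means has half-width t(0.975, 78) × SD × √(2/40) = 1.991 × 0.2236 × SD = 0.445 SD. For assumed SDs of 1.5 and 2.5 points on a 0–10 item, that is 0.67 and 1.11 points. These figures describe a possible new item. They do not measure any fault in the plan as written.

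**Step 6. Count the comparisons.** Section 7 lists POSAS at 6 weeks, POSAS at 3 months, VSS, leakage area, dehiscence, superficial infection and dermatitis: seven. A satisfaction measure would make eight. None of the seven changes in definition, timing or analysis if satisfaction stays unlabelled.

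**The case for a change.** The best argument for a change is that the cost is close to nothing. If POSAS was meant, one sentence would say so. If it was not, one patient-rated question could be added at a visit that already takes place. The link to POSAS is also weaker than it looks: the designated result is a total, Section 8 presents it as scar assessment, and no patient-rated part is named. A scar total is not self-evidently a measure of satisfaction.

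The textual part of this stands. Nothing in the protocol labels a satisfaction measure, and a report that presented the POSAS total as satisfaction would go beyond the plan.

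The case for amending does not follow from it. Naming a POSAS part depends on the content of the scale, which the protocol does not describe. A new item would be an ad hoc question put to patients for whom no blinding is stated, and its result could only be read descriptively. Added part-way through, it would miss patients already seen, so the 0.445 SD half-width would be optimistic. It may also be too late, since Sections 6, 8 and 10 are written largely in the past tense. The remaining option is to draw no conclusion about satisfaction, and that is already consistent with Sections 2 and 7, which promise none.

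**Conclusion.** No change is needed. The observation is accurate but editorial: a motivating question in the rationale was not carried into the objectives. Its effect on the prespecified results is nil. All seven listed comparisons, including the primary one, keep their meaning.

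The 7.0% to 9.75% range should not be attached to this plan. It rests on assumed correlations and on a choice between two results that Section 7 has already ranked.

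The conclusion rests on two points. The first is that Sections 2 and 7, rather than the rationale, define what the trial undertakes to show. The second is that the report will keep to them, presenting POSAS as a scar outcome and making no separate satisfaction claim. An analyst following the plan would do that without further instruction. POSAS as the intended answer to the satisfaction question is plausible but not established, and the conclusion does not depend on it.

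### Section 7 names only superficial infection as a wound complication, so a deep wound or joint infection could go uncounted in either arm

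*Combined protocol and SAP*

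**What the plan says.** Section 7 gives the complication outcome in one line: "Wound complications: dehiscence, superficial infection, allergic contact dermatitis". It has no category for other events and no wording to mark the list as illustrative.

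Three other places bear on the scope:

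- Section 1, on existing closure methods, says "these methods have the same disadvantages: wound discharge, which may lead to infection, wound separation, and the need for wound dressing". Infection is not qualified by depth here.
- Section 1, in its study question, includes the words "wound complications such as wound oozing, wound separation, superficial wound skin infection, and contact dermatitis different". Infection is limited to superficial here, although the list is introduced as examples.
- Section 2 sets the secondary objective: "To compare Vancouver Scar Scale scores, wound leakage area (mm²), wound complications, and allergic contact dermatitis". Complications carry no definition and no depth limit.

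Section 8 describes a 2-week visit for dressing leakage and a 6-week visit for the scar scores. Neither is said to include an assessment for infection. Section 7 also lists POSAS at 3 months, the latest time point in the protocol. No section mentions deep infection, joint infection, reoperation or readmission, and there is no safety-reporting section.

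**The concern.** The word superficial sets a depth limit. Applied as written, the outcome counts a mild skin infection as a complication and leaves out a worse infection in the same wound. A return to theatre for the wound without dehiscence also fits no listed category.

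Both arms close a wound over a knee prosthesis, so a deep or joint infection is among the most serious wound events that could occur. Readers will look to the complication line for harms. If it omits such cases and nothing else in the plan requires them to be reported, the published rate could be too low in one arm or both. Counting a case once it has occurred would then be an unplanned decision.

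**Working it through.** **How cases are classified under the Section 7 list as written**

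| Case | Counted? |
|---|---|
| Superficial infection | Yes, as infection |
| Deep or joint infection, wound also dehisced | Yes, but only as dehiscence |
| Deep or joint infection, wound intact | No |
| Return to theatre for the wound, no dehiscence or other listed event | No |

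The other outcomes do not fill the gap. Leakage area is a count of stained grid squares on the dressing at 2 weeks, and POSAS and VSS are scar scores. None of them records an infection.

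**Size**

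The plan states no infection rate, so there is no figure to reproduce. Section 3 describes a "randomized controlled parallel-group study with 80 participants randomized 1:1", which gives 80/2 = 40 per arm. One uncounted case is 1/40 = 2.5 percentage points of an arm's complication rate.

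The deep-infection risk p is an assumption, shown as a range. Expected cases per arm are 40 × p. The chance of at least one case among all 80 is 1 − (1 − p)^80.

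| Assumed p | Expected per arm | Chance of at least one in 80 |
|---|---|---|
| 0.5% | 0.2 | 33% |
| 1% | 0.4 | 55% |
| 2% | 0.8 | 80% |
| 3% | 1.2 | 91% |

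**What a test could show**

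Section 9 plans "Categorical outcomes: chi-square or Fisher's exact test" at the 0.05 level. Sidedness is not stated, and two-sided is assumed here. With 0 of 40 in one arm, Fisher's exact test gives p = 0.055 for 5 of 40 in the other and p = 0.026 for 6 of 40. Six cases against none are therefore needed.

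As an illustration, suppose one arm has 1 superficial and 2 deep infections, with the wounds intact, and the other has 1 superficial infection. The infection item as written shows 1 v 1 (p = 1.00). Infection of any depth shows 3 v 1 (p = 0.62). The test conclusion is the same, but two serious events appear in the second count and are absent from the first.

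**The case against.** The strongest reply is that the narrow scope looks deliberate. The study question in Section 1 also names superficial infection, so it agrees with Section 7. The unqualified mention of infection in Section 1 describes the drawbacks of other closure methods and does not define this trial's outcome. Patients are randomized after subcuticular suturing (Section 8) and the arms differ at the skin surface, so a focus on superficial events can be defended. This stands in part: Section 1 cannot be used to show an internal contradiction, and the point does not rest on one.

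A second reply is that the protocol never says how a deep infection would be handled. Section 2 is unrestricted, the list in Section 1 is illustrative, staff might record a case anyway, and a case that opened the wound could count as dehiscence. This also stands. A reader might infer that every deep infection would be entered as no infection, but the documents do not say so. They support only that such a case is not named and, on a literal reading, is not counted.

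A third reply is that the omission applies equally to both arms and that few events are expected. That is correct, and it limits the consequence. It does not remove the under-reporting of absolute harm.

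Finally, no complication of any kind has stated criteria, an assessor or an assessment window. That is a wider gap, and a change of wording alone would not close it.

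**Conclusion.** The point holds as a gap in a secondary outcome. The list is closed, its infection item is limited to superficial, and nothing else in the protocol captures a deep wound or joint infection that leaves the wound intact. The complication result could therefore understate harm in either arm, by 2.5 percentage points of an arm's rate per uncounted case. Whether any case occurs depends on a rate that the documents do not give. Over the assumed 0.5% to 3%, the chance of at least one in the trial runs from 33% to 91%.

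Two stronger readings are not supported. A reader might infer that one arm would be made to look safer. That requires deep infections to fall unevenly between the arms, and nothing in the documents shows that they would. A reader might also take the complication line as the trial's only safety measure. Leakage area is a separate wound outcome, although it cannot register an infection.

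The primary POSAS comparison at 6 weeks is unaffected. The benefit of a change is complete by-arm reporting of rare, serious events. It would not give a powered comparison. Because the cost is so low, the change should be made.

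**What to change.** In Section 7, replace the infection item with *any surgical-site infection, reported by depth (superficial; deep or joint)* and add *return to theatre for the wound*. Use matching wording in Section 2.

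Record these at the existing follow-up contacts through the last one, at 3 months. Section 8 lists only the 2-week and 6-week visits, so it should be extended to show the 3-month contact that POSAS in Section 7 already implies. State the criteria for each component and who applies them, so that depth is judged in the same way in both arms.

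In Section 9, say that each component, and the number of patients with at least one event, will be reported descriptively by arm, and that a non-significant test will not be read as evidence of equal safety.

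The cost is a few lines of text and one or two form fields. No visit or procedure is added, provided that the 3-month contact takes place as Section 7 implies. The reported complication rate may be slightly higher.
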